### **International validation of the Colostomy Impact Score**

**Objectives:** To study the influence of diversity in demographic, religious and socioeconomic factors as well as everyday stoma care on CI-score and HRQoL between countries and cultures.

Furthermore, to study the reliability and validity of the CI-score in different countries (Australia, Brazil, China, Denmark, Egypt, Israel, The Netherlands, Lithuania, Portugal, Russia, South Africa, Spain, Sweden, Turkey and the UK) by testing the CI-score against validated measures of quality of life and including test-retest reliability.

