*Content validity:* Comprehensiveness and relevance of the questions in the CI-score have been ensured with the way of the development of the CI-score with the starting point in a Basic Stoma Questionnaire developed by an expert group supplemented by patients ensuring that all possible factors affecting stoma function/impact was included before regression analysis lead to the seven weighed questions. After translation and cross-cultural adaptation face-validity of each translated CI-score will be assessed again by the collaborators before inclusion of patients.

*Construct validity:* This will be tested with hypothesis-testing. The following a priori formulated hypotheses on the construct validity will be tested:

- With a cut-off at 10 point the CI-score will have a sensitivity of at least 85% and a specificity of at least 50% of identifying patients with substantial colostomy impact as measured by the anchor questions (Anchor 1: poor/very poor satisfaction, remaining: Some/major impact).
- Patients with a CI-score of  $\geq 10$  have significant higher scores than patients with CI-score of  $< 10$  on all scales on the EORTC-QLQ-C30 questionnaire and this difference is clinically relevant in global health status, role functioning, social functioning and fatigue.
- Patients with a CI-score of  $\geq 10$  have significant higher scores than patients with CI-score of  $< 10$  on all scales on the EORTC-QLQ-CR29 and this difference is clinically relevant in stoma care problems.
- Patients with a CI-score of  $\geq 10$  have significant worse index value in the EQ-5D-L compared to patients with a CI-score of  $< 10$ . The sensitivity and specificity are expected to be comparable to when comparing to the anchor questions (hypothesis #1).
- The sensitivity and specificity are expected to be the same across all countries performing the validation.
- Men and women have the same relation between CI-score and HRQoL.
- If stoma care products confer a financial burden on the household the CI-score will show poorer correlation with HRQoL compared to patients where stoma care products do not confer a financial burden on the household.
- If the patients' religious affiliation or practice conflicts with having a colostomy, the CI-score will have a poorer correlation to HRQoL compared to patients who are not religious or if their religious practice does not conflict with having a stoma.

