- Patients who had their colostomy in the acute setting will have a poorer correlation between CI-score and HRQoL compared to patients operated in an elective setting.
- Patients who postoperatively had serious complication to their surgery (Clavien-Dindo  $\geq$  IIIb) will have a poorer correlation between CI-score and HRQoL compared to patients with no or minor complications.
- The following hypotheses on differences in HRQoL between different groups will be tested:
- Women colostomates have inferior HRQoL than men
- Obese patients ( $BMI \geq 30 \text{ kg/m}^2$ ) have inferior HRQoL than patients with a  $BMI < 30 \text{ kg/m}^2$
- Patients who perform their everyday stoma care themselves have a better HRQoL than patients who require help.
- Patients using irrigation for their stoma care have a better HRQoL than patients who do not irrigate.
- Patients who report the costs for stoma care products confer a burden on their household finances have an inferior HRQoL than patients who do not report this.

- Patients who report having the possibility to see a stoma care nurse if necessary have better HRQoL compared to patients who report not having this possibility.
- Patients who have had surgery in relation to their stoma for any reason have inferior HRQoL than patients who have not have surgery to their colostomy.
- Patients who report having a bulge in relation to their colostomy have inferior HRQoL than patients who do not report having a bulge.
- Patients who believe they have a hernia in relation to their colostomy have inferior HRQoL than patients who do not report having a hernia.

For convergent validation the CI-score will be tested against 5 anchor questions (not validated) and the EORTC QLQ C30+CR29 (validated). Cross-cultural validity: See translation section.

*Reliability:* For a randomly selected subgroup in each country the CI-score and anchor question will be administered twice with an interval of approximately 2 weeks. The two administrations will be independent and both the setting when answering and the forms of administration will be similar for the individual patient. For ensuring stable patients an extra question on recent changes in stoma function will be added to the retest.

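### Nine group comparisons placed under the CI-score's construct validity do not involve the CI-score, and no hypothesis or clearly stated analysis takes the score as the outcome of those patient and stoma-care factors

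*Combined protocol and SAP*

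**What the plan says.** Under Material and methods, the construct-validity paragraph opens its list with "The following a priori formulated hypotheses on the construct validity will be tested". The bullets that follow deal with the CI-score: its accuracy at the cut-off of 10, differences between patients above and below that cut-off, and its relation to HRQoL in subgroups.

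Partway down, a further bullet serves as a second lead-in: "The following hypotheses on differences in HRQoL between different groups will be tested". Nine comparisons follow. A typical one reads: "Patients who report having a bulge in relation to their colostomy have inferior HRQoL than patients who do not report having a bulge". None of the nine mentions the CI-score.

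The Objectives set a wider question. They ask about the influence of demographic, religious and socioeconomic factors and of "everyday stoma care on CI-score and HRQoL between countries and cultures". Aim 3, at the end of the Background, likewise names the CI-score or HRQoL as what stoma care and costs might affect. Aim 1 speaks of stoma impact and HRQoL.

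The Statistical analysis section is run country by country. Its one general regression sentence refers to univariate regression, description and an estimate of impact on HRQoL. It names no analysis in which the CI-score is the outcome of a patient or stoma-care factor.

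**The concern.** A construct-validity hypothesis should be able to fail because the instrument is poor. A comparison of HRQoL between patients with and without a bulge cannot fail for that reason. It tests a belief about bulges and HRQoL, and the CI-score plays no part in it.

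Two things are at stake. First, if these nine results were reported as validity evidence, the score would be credited or penalised for something it did not do. Second, the informative version of the same comparisons is missing. Groups such as patients with a bulge, a hernia, stoma surgery or a need for help with care are natural known groups for a stoma-impact score, and the plan never asks whether the score separates them. That omission also leaves the CI-score half of the objective without a clear analysis.

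**Working it through.** The plan gives no figure of its own on this point, so the check is a count and a comparison of sections.

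**Step 1: count the hypotheses.** The lead-in bullet is not itself a hypothesis and is left out.

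- *CI-score involved (10):* accuracy against the anchors; QLQ-C30 by CI group; CR29 by CI group; EQ-5D index by CI group; equal sensitivity and specificity across countries; same CI-HRQoL relation in men and women; and a weaker CI-HRQoL correlation with financial burden, with religious conflict, after acute surgery and after serious complications. The cross-country bullet does not name the score, but the accuracy it refers to is the score's.
- *HRQoL only (9):* sex, BMI, self-care, irrigation, cost burden, nurse access, stoma surgery, bulge, hernia.

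10 + 9 = 19, and 9/19 = 47%.

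**Step 2: does the CI-score enter the nine indirectly?** Data analysis measures HRQoL by the anchor questions, the QLQ-C30 and the CR29, and one hypothesis adds an EQ-5D index. All are separate from the CI-score. If every patient's CI-score were replaced by a random number, all nine results would be unchanged.

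**Step 3: look for the CI-score as the outcome of a patient or stoma-care factor.**

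- *Hypotheses on accuracy and CI groups:* the score is the classifier, not the outcome.
- *Hypotheses on sex, finances, religion, acute surgery and complications:* these factors modify the CI-HRQoL relation. That is a different question from the level of the score. If a factor adds a constant c to every score in one group, the within-group correlation does not move: corr(CI + c, HRQoL) = corr(CI, HRQoL).
- *Statistical analysis:* it plans correlations of the score with anchors and EORTC results, mean QLQ-C30 by CI group, a Mann-Whitney test of CI-score, and a 2 by 2 table. The Mann-Whitney test does compare CI-scores, but between anchor-defined HRQoL groups. Irrigation and bag-change frequency are compared between countries. The regression sentence names only HRQoL.

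Hypotheses found with the CI-score as the outcome of such a factor: 0. Explicit analyses: 0.

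**Step 4: which HRQoL measure do the nine use?** None of the nine says. The candidates are the anchors, QLQ-C30, CR29 and the EQ-5D index. The 10-point difference in the sample-size text belongs to an EORTC score that is not further specified, so it does not settle the choice.

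**Step 5: cost of adding the CI-score comparisons.** Nine per country over 15 countries is 9 × 15 = 135. At the 0.05 level used for the sample size, and if no factor had any relation to the score, the expected number of chance findings is 9 × 0.05 = 0.45 per country and 135 × 0.05 = 6.75 overall. Power cannot be computed, because the documents give neither an SD nor a relevant difference for the CI-score.

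**The case against.** The strongest reply is that the nine were never offered as evidence for the score. They have their own lead-in, parallel in form to the first but on a different subject, and a lead-in printed as a bullet suggests that list levels were lost. On that reading they form a second block serving aims 1 and 3. This is plausible and it stands. What remains is that the block sits in the construct-validity section with no other label.

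A reader might infer that nearly half of the validity evidence is void, or that confirming the nine would inflate the overall verdict on the score. The documents do not support that. They set no threshold, tally or pooled rule for confirmed hypotheses, and the validation analyses that are spelled out all use the CI-score.

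A reader might also infer that the plan excludes any analysis of influences on the CI-score. That too goes too far. An aim to identify factors is exploratory and needs an analysis rather than a directional hypothesis. In the regression sentence it is unclear whether HRQoL governs all three items or only the last. The fair statement is that no such analysis is explicit.

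Two smaller points stand. Sex and cost burden also appear as modifiers of the CI-HRQoL relation, so knowing how HRQoL differs by them helps to interpret those tests. And the seven CI items are not listed in the documents, so the number of the nine factors that are independent of the score is unknown.

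**Conclusion.** The point holds in a limited form. Nine of the 19 listed hypotheses do not involve the CI-score and cannot bear on its validity. The objective's question about influences on the score has no matching hypothesis and no explicit analysis. The nine remain useful for the HRQoL side of aims 1 and 3, and the ten CI-score hypotheses are unaffected.

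The 47% describes the make-up of the list. It is not an estimate of bias in the validation conclusion. The verdict rests on the two lead-ins and their bullets as printed, and on the regression sentence being read at face value. If the nine were always meant as a separate block, the labelling part shrinks to a clarification, but the missing CI-score analysis remains. It is worth acting on, because the known-groups evidence is available from data the study must collect anyway.

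**What to change.** 1. Run the same nine group comparisons with the CI-score as outcome. Test the total score, for instance with the Mann-Whitney test the plan already uses for it, and report the proportion scoring 10 or more alongside. Before analysis, state the expected direction for each factor. Use those with a clear direction as known-groups tests and report the rest as descriptive. Flag or exclude any grouping factor that is itself one of the seven CI items.
2. Move the HRQoL versions under aims 1 and 3, name one HRQoL measure for all nine in advance, and state that they are not counted as validity evidence. Any single pre-named measure meets the point. If the 10-point difference is to be used with it, say which EORTC scale it refers to.
3. Acknowledge the added multiplicity, and report estimates with confidence intervals.

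The cost is protocol wording and nine more comparisons per country. No new patients or questionnaires are needed. If the proportion scoring 10 or more were formally tested as well, the number would be 2 × 9 = 18 per country, which is why it is better kept descriptive.

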#### **Material and methods:**

International validation will be conducted as a retrospective cohort study. Local health care professionals will identify includable patients and register relevant clinical information on each patient from the hospital chart. Most centres will include patients from national or regional databases, some will however include conveniently if a database is not available. Our international collaborators will be responsible for sending out and collecting the questionnaires and returning the completed questionnaires to the undersigned. In countries with sufficient internet accessibility and -infrastructure the data collection will be web based i.e. patients are sent a link to the redcap-database for them to enter their answers directly. Some centres will employ paper versions of the questionnaires. In areas with substantial number of illiterates investigator led interviews can be performed.

**Inclusion criteria:** Patients who were operated with curative intent for rectal cancer with APE, Hartmann's procedure or pelvic exenteration will be included retrospectively aiming at 250 patients from each of the participating countries. This number is based on a calculation of strength based on the results from the development of the CI-score. (mean EORTC score in the major CI-group: 72. SD: 22. Minimal clinical difference: 10 points. Alpha: 0,05 STATA => sample size 206 patients. Expected dropout: 20%). Accessibility to cohorts of interest may differ between countries. Therefore, number of patients and mode of contact to patients should be agreed by the local investigation and the steering group in the planning of the data collection and included as individual amendment to the final protocol. In Denmark patients operated from January 1st 2001 to December 31st 2016 will be included.

**Exclusion criteria:** Age less than 18 years, known disseminated or recurrent disease, mental dementia and the inability to understand the actual language.

As the CI-score is a construct based on a formative model, statistical analysis based on the Classical

Test Theory (CCT) and Item Response Theory (IRT) cannot be applied. However, the following aspects of validity and reliability from the COSMIN checklist can and will be evaluated:

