#### Data analysis:

Construct validity: Convergent validity will be studied by testing the CI-score on APE/Hartmann-patients against two measures of HRQoL; the anchor-questions assessing the overall stoma-impact on HRQoL, the EORTC QLQ C30 questionnaire version 3.0 and the EORTC QLQ CR29. Construct validity will furthermore be assessed by hypothesis-testing assessing the direction and magnitude of the expected correlations. Test-retest reliability will be studied on a subgroup in all included

countries. Also, we will include questions on background demographics, socioeconomic status, everyday stoma care and -costs thereby enabling investigation of the practical and economic aspect of living with a stoma varying from country to country.

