#### Statistical analysis:

Statistical analysis will be performed separately for each country.

The correlations between total CI-score, anchor questions and the EORTC questionnaire results will be calculated for all participating patients according to the guidelines for the scores. For each CI-score group (minor CI/major CI) the mean EORTC QLQ C30-score will be calculated, testing the overall difference of impact on HRQoL between the CI-score groups.

Using the anchor-questions, the patients are divided into two HRQoL groups of those reporting no/minor or some/major impact on HRQoL. Relationship between CI-score and HRQoL group will be illustrated in box-plot for each country, where we expect statistically significant differences in median CI-score between the two HRQoL groups. Differences will be tested by Mann-Whitney U test. A contingency 2 by 2 table will be used to assess the degree of agreement between the two CI-score groups and the two HRQoL groups. Based on this, the sensitivity for the score will be calculated for each country. The added questions about irrigation and stoma-bag change frequency will be compared country-wise. Univariate regression analysis, descriptive analysis and estimation of impact on HRQoL will be performed. Test-retest reliability will be evaluated using Intraclass Correlation Coefficient and Cohens' Kappa.

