#### Organisation:

This project will outgo from the Research Unit, Department of Surgery, Aarhus University Hospital. Within recent years we have achieved profound experience with patient reported outcome measures (PROMs). Recently, a multidisciplinary clinic for cancer survivorship and late sequelae to cancer treatment has been established in relation to the Pelvic Floor Unit, Aarhus University Hospital. We have established cooperation with colleagues in the countries mentioned and we have written consent that they will assist us in retrieving data on retrospective cohorts in their respective countries as described above. To support the data collection and project logistics, each collaborating site (excluding Australia, Brazil, China, Egypt, Israel and Turkey) will receive a site visit

form the lead centre in the initial project phase.

Primary publications on validation of the CI-score will outgo from the Research Unit, Dept. of surgery, Aarhus University Hospital in accordance with the following authors' agreement:

The international validation of the CI-score is a collaboration of researchers from 15 countries worldwide and to carry out the project more than one collaborator is needed in most countries. This compiles to a comprehensive list of names. Therefore, the output from the primary validation study as stated in this protocol will be published under the authorship of [name], [name], [name], [name], [name], [name] and the "International Collaborative Group for the Colostomy Impact Score Validation". All collaborators will be registered as authors and be PubMed searchable and citable.

It is expected that the collected data will produce ideas and new research questions might emerge from the data itself. The local collaborators are encouraged formulate new research questions and protocols regarding their national cohorts. In agreement with the steering group, such research can be published with a local investigator as first author and member(s) of the steering group as co-authors in accordance with individual agreements.

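### Nine HRQoL hypotheses are analysed country by country with no named outcome and no between-country test, so the results cannot show whether a factor's effect differs between countries

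*Combined protocol and SAP*

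**What the plan says.** The construct-validity part of Material and methods ends with a list introduced by "The following hypotheses on differences in HRQoL between different groups will be tested". It has nine entries: sex, obesity, self-care, irrigation, cost burden, access to a stoma nurse, stoma-related surgery, bulge and hernia. Each predicts a direction, for example "Women colostomates have inferior HRQoL than men". None names a scale or a size of difference.

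The Statistical analysis section opens with "Statistical analysis will be performed separately for each country". The Organisation section states that "The international validation of the CI-score is a collaboration of researchers from 15 countries worldwide", and the list of countries under Objectives also counts to 15.

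HRQoL is measured in several ways. Data analysis sets the CI-score "against two measures of HRQoL; the anchor-questions assessing the overall stoma-impact on HRQoL" and then goes on to name the QLQ-C30 and the CR29. Statistical analysis forms two HRQoL groups from the anchor questions, but also says that for each CI-score group "the mean EORTC QLQ C30-score will be calculated, testing the overall difference of impact on HRQoL". One of the CI-score hypotheses in Material and methods uses an EQ-5D index. All of these statements concern the CI-score; none fixes the outcome for the nine group comparisons.

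The only significance level in the plan is in the sample-size note: "Alpha: 0,05 STATA => sample size 206 patients". No section gives a pooled test, a test of differences between countries, a multiplicity rule or an exploratory label for the nine.

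**The concern.** The first aim in the Background asks which demographic and socioeconomic factors influence HRQoL. The third asks whether differences in stoma care and costs across countries affect it. The Objectives phrase the question as one between countries and cultures.

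Fifteen separate analyses answer a different question: in which national samples does a factor reach significance? Some countries will be significant and others not when the factor has no effect anywhere, when it has the same effect everywhere, and when its effect truly varies. The planned output cannot tell these apart. A mixed pattern invites a cultural explanation, and nothing in the plan guards against that. Leaving the outcome open makes it worse, because a result on any of several instruments could be taken as support.

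**Working it through.** **Inputs from the plan.** Nine hypotheses; 15 countries; alpha 0.05; SD 22 ("mean EORTC score in the major CI-group: 72. SD: 22"); a minimal clinical difference of 10 points; a target of 250 per country with 20% dropout, so 250 × 0.80 = 200 evaluable.

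**Assumptions.** Tests are two-sided, since sidedness is not stated. The 5% level applies to the nine hypotheses. The share of patients with a factor is not given, so splits of 50:50, 20:80 and 10:90 are shown.

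**The plan's own figure.** A two-sample t-test for 10 points with SD 22, two-sided 5% and equal groups needs 102.7, rounded up to 103, per group for 90% power: 2 × 103 = 206. The plan's 206 is reproduced. The 90% power is inferred, because the plan states none; 80% power gives 154.

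**Chance findings, one outcome per hypothesis.**
- Tests: 9 × 15 = 135.
- One null factor, significant in its predicted direction in at least one country: 1 − 0.975^15 = 0.316, or 32%. In either direction: 1 − 0.95^15 = 0.537, or 54%. Countries are separate samples, so independence is reasonable here.
- All nine null: 135 × 0.025 = 3.4 false confirmations in the predicted direction; 135 × 0.05 = 6.75 in either direction. These expectations do not need independence.
- Half of the 135 nulls true: 3.375 / 2 = 1.7 in the predicted direction.
- Outcome left open: if any one of several measures could confirm a hypothesis, simulation with correlations of 0.3 to 0.7 between measures gives about 6 of 135 for two measures and about 9 to 12 for four, all nulls true. The number of measures and the correlations are assumptions.

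**One common effect in every country.** SE = 22 × √(1/n1 + 1/n2) with n1 + n2 = 200. Power ≈ Φ(difference/SE − 1.96). Expected number of significant countries = 15 × power.

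| True difference | Split | SE | Power | Significant countries of 15 |
|---|---|---|---|---|
| 10 | 50:50 | 3.11 | 0.895 | 13.4 |
| 10 | 20:80 | 3.89 | 0.73 | 10.9 |
| 10 | 10:90 | 5.19 | 0.49 | 7.3 |
| 5 | 50:50 | 3.11 | 0.36 | 5.4 |
| 5 | 10:90 | 5.19 | 0.16 | 2.4 |

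Even in the most favourable row, the chance that all 15 countries agree is 0.895^15 = 0.19. A mixed picture therefore has probability of about 81% (82% with the t-test) when the true effect is identical everywhere.

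**A stratified analysis of everyone.** With 15 × 200 = 3,000 patients and the same split in each country, a 5-point difference tested at 0.05/9 (the strictest Holm step) has power above 0.99 at 50:50 (SE 0.80), 0.986 at 20:80 (SE 1.00) and 0.83 at 10:90 (SE 1.34).

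**The case against.** The strongest reply is that these are directional predictions made in advance in a non-interventional questionnaire study, and several, such as bulge, hernia or needing help with stoma care, are plausible. Expecting all nine to be null is unrealistic. No entry in the list uses the word significant, no rule for a national verdict is written, and the plan also mentions description and estimation. Validation hypotheses are often judged by direction and size. A pooled test also needs care here, because recruitment (database or convenience) and mode of completion (web, paper or interview) differ between countries.

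Much of this stands, and it rules out stronger readings that a reader might infer:
- That several national confirmations will be false. This requires all nulls to be true; the count falls to about 1.7 of 135 if half are.
- That 135 tests at 5% are planned. The level comes from the sample-size note, and its use for the nine is an assumption.
- That any scale of any instrument is an admissible outcome. The documents leave the outcome unspecified, which is not permission to choose freely. Multiplying 135 by four outcomes would count tests rather than confirmed hypotheses, and the four is not in the plan.
- That the authors will read differing significance as cultural difference. The aims make this a plausible risk; no section says it will happen.

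The reply does not reach the central point. The nine are to be tested, no magnitude is set for them, and Data analysis ties direction and magnitude to correlations rather than to these group differences. Realistic, non-null factors do not help either: a common true effect is exactly the case in which separate analyses give a mixed picture. Differences in recruitment and mode are a reason to stratify by country and to test heterogeneity. They do not make separate verdicts informative about differences between countries.

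**Conclusion.** The concern holds in this form: for the nine HRQoL hypotheses the plan leaves the outcome unspecified and has no analysis able to show whether a factor's effect differs between countries, which is part of what the study sets out to learn. At two-sided 5% on one outcome, a null factor has a 32% chance of a predicted-direction finding somewhere, and 1.7 to 3.4 false confirmations are expected if half to all of the nulls are true. A uniform 10-point effect would be significant in about 13 countries at a 50:50 split and about 7 at 10:90.

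These figures rest on the 5% level applying, SD 22 holding in every country and for every factor, and 200 evaluable patients per country. Material and methods allows country sizes to vary by local amendment; that changes power but not the false-positive counts. The CI-score validation hypotheses are a separate matter and are not affected by this point.

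**What to change.** In Statistical analysis, add for each of the nine hypotheses:
- one pre-specified HRQoL outcome. QLQ-C30 global health status is one candidate, since Material and methods already names it among the scales where a clinically relevant difference is expected; any single scale fixed in advance would serve;
- one country-stratified analysis of all patients on that outcome, with a factor-by-country heterogeneity test;
- country estimates with confidence intervals, presented as descriptive and without a verdict for each country;
- other HRQoL scales labelled as supportive.

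A Holm adjustment over the nine pooled tests is an option, not a requirement; statisticians could reasonably differ on it in a study of this kind. If it is not used, the plan should say so.

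The cost is wording and a little more analysis work on data already being collected. The downside is that country-level results become descriptive.
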